## **Major Analytic Methods Proposed (Including Statistical Design and Power)**

### ***Specific Aims***

**Aim 1.** To adapt CIFFTA and the assessment instruments necessary to test its efficacy to the unique Haitian sociocultural contexts. This process of adaptation has the purpose of optimizing CIFFTA's acceptability and cultural appropriateness. It will rely on ethnographic methods (participant observations, focus groups, and interviews) to guide the adaptation process.

**Aim 2.** Determine, via a pilot efficacy trial, the impact of CIFFTA compared with standard-of-care for reduction of drug use, risky sexual behaviors and delinquency risk among Haitian adolescents ages 13 to 17 in Miami-Dade County. The ethnographic component of the study will monitor the delivery of the intervention, collecting process data and affording the investigators needed perspective on the intervention's impact.

**Aim 3.** To generate preliminary data on the usefulness of assessment tools and CIFFTA's efficacy among the population. These data will help evaluate the effect of the intervention and its best form of implementation. They will also provide preliminary evidence to justify a full clinical trial of CIFFTA in a population of Haitian youth at risk.

### ***Analytic Methods***

Latent Growth Modeling within a Structural Equation Model (SEM) framework. We will conduct latent growth curve analyses using Stata 14 gsem (1), SAS Proc Mixed (2), SPSS Mixed Models, and/or Mplus 8 (3) to compare the trajectories of participants in CIFFTA to those in TAU. Given that the data are balanced and have more than 2 time points, the model is identified, thereby allowing us to perform SEM growth curve analysis (4). These models conceptualize each component of growth (the baseline/intercept, the slope/rate of change, the quadratic slope, etc.) as composed of a fixed and random effect. Thus, these models have multiple components of variance as well as a regression-type model of the underlying mean growth curves of the two groups. Within an SEM framework, growth curves are treated as latent (unobserved) variables influenced by occasion- and individual-level covariates, allowing us to explicitly model growth trajectories overtime.

Specific analysis link functions will be matched to fit the distribution of each outcome variable. For ordinal outcomes (e.g., frequency of drug/alcohol usage), we will use an ordinal logistic regression function. The proportional odds assumption will be evaluated using the Brant test, and if needed, addressed by allowing problematic coefficients to vary across levels of the outcome variable. Count outcome measures (e.g., number of sexual partners, problem behaviors, re-arrests) will be analyzed using a negative binomial function rather than Poisson regression to address potential over-dispersion. Vuong tests will be performed to assess whether the data have an excess of zeros, and if necessary, zero inflated negative binomial regression will be used instead.

Analysis for Aims 2 and 3: The first set of analyses will explore the efficacy of CIFFTA compared to SOC in modifying the main adolescent outcomes and to generate effect sizes for a possible full clinical trial: a) drug/alcohol use, b) risky sexual behavior, c) delinquent behavior, and d) recidivism. Latent growth modeling will be used to investigate the efficacy of CIFFTA as compared to SOC. For each model, we will examine the effect sizes to determine the overall impact of CIFFTA over SOC on the outcome variables. We will generate estimates of effect sizes, such as Cohen's d (5), for both rate of change and for the

difference at a particular time between the two conditions (6). Following Cohen's guidelines (5), we will interpret our effect sizes using the convention of "small" ( $d = .2$ ), "medium" ( $d = .5$ ), and "large" ( $d = .8$ ).

Our hypotheses concerning the direct and indirect effects of key variables on drugs/alcohol use, risky sexual behavior, delinquent behavior, and recidivism will be tested using SEM mediation analyses. To test potential indirect relationships we will include several mediators, including family connectedness, acculturation (bicultural involvement scale), and motivation to change. This will allow us to examine whether CIFFTA directly effects our outcomes of interest and/or whether the effect of CIFFTA operates through its effect on family connectedness, acculturation, and motivation to change. These mediation models will enable us to address **Specific Aim #2** by testing the significance of paths in the model linking the intervention variable to the risk-related outcomes in question (both at discrete points in time and as the change index derived from differences in ordinal frequency at baseline and at post-intervention time intervals).

In a separate set of analyses, we will examine the hazard rate of drug/alcohol use and sexual risk behavior during the post-intervention phase of the study. Comparisons across the two intervention conditions will thus be made regarding the hazard rate of having sex during the post-intervention period, sex with multiple partners ( $>1$  per month), and unprotected sexual episodes. Specifically, shared frailty Cox proportional hazard regression will be utilized to examine possible differences in the hazard rate of various risky behaviors (drug- and sex-related) in CIFFTA and control conditions during the post-intervention phase. This will prove particularly helpful in determining the hazard rate for post-intervention sexual initiation or unprotected sex in the two groups being compared, while also controlling for the time-dependence nature of our data. Similar analyses will be performed regarding initiation into drug use and other problem behaviors to determine whether the possible benefits of the CIFFTA approach extend to a range of risky behaviors.

**Power Analysis:** We will recruit 88 participants for this study, with the intention of analyzing data for 80 participants after attrition. The original CIFFTA randomized trial with 28 Hispanic adolescents showed CIFFTA to be more efficacious than the comparison family treatment at: 1) reducing drug use, and 2) improving parenting practices as reported by adolescents (7). More recently, a technology assisted CIFFTA study of 80 minority youth at high risk for drug use showed CIFFTA to be more efficacious in reducing behavior and conduct problems and in improving family cohesion, when compared to a delay treatment condition (8). Based on these findings, CIFFTA was placed on the National Registry of Evidence Based Practices using their more rigorous criteria for entry. Given such consistent findings of efficacy for CIFFTA among Hispanic youth, a sample size of 80 will be sufficiently powerful to detect relatively small effects ( $R^2 = 0.05$ ) at adequate levels of power (0.84 - 0.86) using a relatively simple SEM. A sample size of 80 is also well above sample guidelines for Stage 1 treatment trials (80)). Nevertheless, to deal with attrition, which in the case of Haitian and because of the ethnographer's engagement with the families will not be higher than 10%, we plan a sample of 88 adolescents.

Nevertheless, we recognize and appreciate the limits of estimating simple SEMs, such as ours, with a small sample size. Therefore, we will take several steps to mitigate concerns about statistical power, including: limiting the use of latent variables when possible, constructing parsimonious path models, and using Bayesian estimators. When theoretically and empirically appropriate, we will use principal components factor analysis to combine multiple indicators into a single scale capturing the underlying construct rather than estimating multiple latent variables since the latter often requires larger samples.

The use of such factor-score scales will enable us to conduct simpler pathway analyses with fewer predictors, thereby freeing up additional degrees of freedom. Our path models will be as parsimonious as possible, focusing on key theoretically grounded mediating relationships instead of engaging in exploratory data analysis with numerous pathways. When appropriate, path analyses may be performed separately to increase statistical power. Finally, we will employ Bayesian estimators when possible since they often perform better with small sample sizes (9). Despite these additional steps, we also emphasize that our analyses are preliminary in nature, primarily designed to show initial efficacy in anticipation for the submission of a RO1 grant designed to examine these relationships using a larger sample in a possible full clinical trial (see **Specific Aim # 3**).

**Analysis Rationale:** While there are numerous approaches to analyzing longitudinal data, including hierarchical linear models (HLM), we opted for a SEM approach since it provides greater modelling flexibility and better enables us to test our underlying theoretical model. In contrast to HLM, SEM allows for the simultaneous estimation of multiple growth curves, indirect/direct effects, and multiple indicators of model fit. Mediating relationships can be assessed within a HLM framework using Baron and Kenny's (10) approach, but SEM allows for the decomposition of direct/indirect effects as well as the simultaneous estimation of mediating and moderating relationships (11). Moreover, SEM will allow us to estimate growth-curves and mediating relationships at the same time in a way that HLMs cannot (12). The estimation of indirect effects within a growth-curve framework is especially important for **Specific Aim #2**, as we hypothesize that CIFFTA will not only have a direct effect on our outcome measures, but will also have an indirect effect operating through its effect on family connectedness, acculturation, and motivation to change. The estimation of mediating relationships will provide greater insights into any causal mechanisms (if any) at work, allowing for a more refined application of CIFFTA in a possible full clinical trial. SEM is also better equipped for assessing our theoretical model. In addition to providing measures of statistical significance, SEM generates several useful measures of overall model fit (e.g., CFI, AIC, BIC, etc.) that can be used to evaluate the appropriateness of our theoretical model over alternative models (11). Finally, SEM is better equipped to handle missing data than traditional regression or HLMs as it allows for maximum likelihood or Bayesian estimation (13).

Survival analyses can also be performed within a SEM framework. We will utilize shared frailty proportional hazard Cox regression as it does not make assumptions about the baseline hazard rate like other survival analyses (e.g., exponential, Weibull), while the shared frailty component of the model will allow us to adjust for the dependence of survival times via random effects (12). Survival analysis is ideal for estimating time-to-event data such as the hazard rate of drug/alcohol use and sexual risk behavior during the post-intervention phase. Because our study contains 4 waves, each with their own start/finish date, the data will be right-censored, thereby necessitating the use of survival analysis techniques. While ordinary least squares regression treats censored cases as missing, survival analysis will adjust for censoring when calculating hazard rates, providing more accurate estimates (12).

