This is a multi-wave study, with approximately all the participants recruited by the end of Year 02 and the remainder in the beginning of Year 03. At baseline, we will conduct comprehensive assessments of all study constructs and repeat all other assessments annually. Activities during the first three months will consist of the following: Staffing, Instrument Calibration, Ethnographic Update. Each wave will be composed of 22 participants to be randomized into two groups (11 each). Each undergo assessment at intake (T1) and outtake (T2), a booster session 3 months after outtake and a final assessment at 12 months. Data analysis process will be initiated at the third month and continue throughout the study implementation.

Study Protocol

[figure not shown]
IRB ID: 20180597 (CR00012479)

Study Number: 1 R34 DA043784-01A1

Date: July 19, 2018

Publications are expected to start from month 20. The table below details the activity processes.

Project Timeline

9) Study Endpoints*

Primary outcomes are: intervention attendance and completion; sustained abstinence in substance use through biochemical verification and self-report; family functioning; sexual risk behavior; and conduct disorder.

Secondary outcomes include recidivism in delinquency, improvement in family communication, and peer/gang involvement.

10) Procedures Involved*

RCT procedures

CIFFTA has three major components – Family-Based Therapy, Individual Therapy, and Psycho-educational Modules – delivered over 16 weeks in a six sessions (60 minutes each) per month format. In this study, the therapy will be delivered in the home to reduce missed sessions and premature termination. Special training will focus on how to structure the home environment to reduce distractions. Three sessions per month will typically be a session which may include Family-based Therapy or Psycho-educational modules with the family or parents alone (e.g., parent training). The other three sessions are typically with the adolescent alone and include Motivational Interviewing or Psycho-educational modules designed for the adolescent.

Study Protocol

IRB ID: 20180597 (CR00012479)

Study Number: 1 R34 DA043784-01A1

Date: July 19, 2018

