Youth Urine Toxicology. As part of our research component, we plan to collect voluntary urine specimens for analysis at the times of the youths' initial and follow- up interviews in order to validate self-report. We will follow procedures informed by NIDA's CJDATS workgroup guidelines. Urine specimens will not be collected on youths incarcerated for more than two days. The use of four substances will be probed using the Onsite CupKit® urine screen procedure (positive threshold levels are noted in parentheses): (1) methamphetamines (500 nanograms per milliliter [ng/ml] of urine), (2) opiates (300 ng/ml of urine), (3) cocaine (300ng/ml of urine), and (4) marijuana (THC) (50 ng/ml of urine). The surveillance window for the four drugs is as follows: methamphetamines and opiates = 48 hours; cocaine = 72 hours; marijuana: moderate users = 5 days; heavy users = 10 days; chronic users = 20 days. Although we considered hair analysis, urine screens were selected because of they are the most widely used and accepted method for supervision monitoring (Lipsey & Wilson, 1998), they are minimally invasive, can be collected in the community during follow-up assessments and carry fewer taboos on collection (Meyers et al., 2002). Urine screen results will be kept confidential, and will be collected in containers marked with pre-printed labels without personal identifying information. To assure integrity of the sample, the Onsite CupKit® automatically checks for temperature, and the interviewer will ensure that there is no one else in the restroom.

Overview of Assessment Procedures and Attrition

The 3-month follow-up assessment will be measured from the end of the intervention, as will be the 6-month and the 12-month follow-up

Study Protocol

IRB ID: 20180597 (CR00012479)

Study Number: 1 R34 DA043784-01A1

Date: July 19, 2018

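### The growth-curve efficacy model neither fixes a common baseline for the two arms nor allows a break at the end of treatment, which can cost much of the power of an 80-participant pilot

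*SAP*

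**What the plan says.** - **Efficacy model.** SAP, Analytic Methods, makes latent growth modelling the analysis for Aims 2 and 3. It treats "each component of growth (the baseline/intercept, the slope/rate of change, the quadratic slope, etc.) as composed of a fixed and random effect" and models mean curves for the two groups. It adds: "Given that the data are balanced and have more than 2 time points, the model is identified".
- **Effect measures.** Cohen's d is to be given for the rate of change and for the arm difference at some one time. The SAP does not fix the polynomial order, the time scores, the visit for that difference, or whether the baseline mean is common to the arms.
- **Treatment period.** Protocol section 10, RCT procedures, has CIFFTA "delivered over 16 weeks in a six sessions (60 minutes each) per month format". Section 8 adds one booster session 3 months after outtake.
- **Visits.** Protocol section 10, Overview of Assessment Procedures and Attrition: "The 3-month follow-up assessment will be measured from the end of the intervention". The 6- and 12-month visits use the same clock. Section 8 instead lists intake, outtake and 12 months.
- **Randomisation.** Protocol section 10, Study Process, places it after baseline data are logged.
- **Size.** SAP, Power Analysis, holds that "a sample size of 80 will be sufficiently powerful to detect relatively small effects". The effect meant is an R² of 0.05, and the power claimed for it is 0.84 to 0.86.

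**The concern.** The weekly treatment lies wholly between baseline and the first follow-up, but a growth slope spreads its effect over about 16 months. If benefit is gained by the end of treatment and then holds or fades, a slope is a poor summary of it, and a curve with no break can misplace the arm difference at individual visits.

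Separately, randomisation after baseline means that any true baseline difference between arms is zero. A model that estimates one anyway spends information on a known quantity. Growth models do this by default unless the arm effect on the intercept is fixed at zero, and the SAP does not say that it will be.

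Aim 3 is to produce effect sizes for a full trial, so both the power of this pilot and the d values carried forward are at stake.

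**Working it through.** **The plan's own power figure.** R² = 0.05 gives f² = 0.05/0.95 = 0.0526, and d = 2√0.0526 = 0.46 for a 1:1 comparison. With N = 80 the noncentrality is 80 × 0.0526 = 4.21, and √4.21 = 2.05. Two-sided 5% power is Φ(2.05 − 1.96) = 0.54 (0.53 by the F test), so the stated 0.84–0.86 does not reproduce. That is a separate matter. It is noted here because d = 0.46 is used below.

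**Inputs.** From the documents: 40 per arm; visits at baseline and 3, 6 and 12 months after a 16-week (3.7-month) treatment, so t = 0, 6.7, 9.7, 15.7 months. Assumed, because the documents give none of them: two-sided α = 0.05; SD 1; equal visit correlation ρ = 0.3, 0.5 or 0.7; complete data; continuous outcome; known covariance; and three effect shapes (sustained 1, 1, 1; fading 1, 0.8, 0.5; widening linearly to 1 at the last visit), each multiplied by 0.46.

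**Straight-line fit to a sustained effect.** True differences are 0, 1, 1, 1. Mean t = 8.025 and Sxx = 127.87. Slope = 8.025/127.87 = 0.0628; intercept = 0.75 − 0.0628 × 8.025 = 0.25. Fitted differences are 0.25, 0.67, 0.86, 1.23. A quadratic gives 0.01, 0.92, 1.09, 0.98, an error of 9% or less.

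**Power formulas, worked at ρ = 0.5, sustained effect.**

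1. Slope, free intercept per arm: variance = (2/40)(1 − ρ)/Sxx = 0.05 × 0.5/127.87, SE 0.01398. Slope difference = 0.46 × 0.0628 = 0.0289. z = 2.065; power = Φ(0.105) = 54%.
2. Slope, common baseline: t′V⁻¹t = [Σt² − ρ(Σt)²/(1 + 3ρ)]/(1 − ρ) = (385.47 − 206.08)/0.5 = 358.8; SE = √(0.05/358.8) = 0.0118. Slope per unit effect = [32.1 − 0.2 × 32.1 × 3]/0.5 ÷ 358.8 = 0.0716; times 0.46 = 0.0329. z = 2.79; power = 80%.
3. Average of three follow-ups, common baseline: variance = 0.05 × [(1 + 2ρ)/3 − ρ²] = 0.05 × 0.4167, SE 0.144. z = 0.46/0.144 = 3.19; power = 89%.

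**Power (%) at ρ = 0.3/0.5/0.7**

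| Effect shape | Slope, free intercepts | Slope, common baseline | Visit average, common baseline |
|---|---|---|---|
| Sustained | 41/54/76 | 79/80/88 | 87/89/96 |
| Fading | 13/17/25 | 42/37/40 | 66/69/81 |
| Widening linearly | 43/55/77 | 65/70/84 | 56/58/71 |

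The quadratic's 2-df growth test with free intercepts gives 46/60/83% for the sustained effect, so it repairs most of the misfit but little of the power.

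A common baseline does not by itself cure the straight-line misfit. At ρ = 0.5 the slope of 0.0716 per month implies 0, 0.48, 0.69, 1.12 (0.0716 × 6.7, 9.7, 15.7) for a true 0, 1, 1, 1.

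**Sensitivity.** Adding an end-of-treatment visit, with d = 0.5 and ρ = 0.5, the free-intercept slope has power 47% against 96% for the common-baseline average (sustained). For an effect of 0.5, 0.4, 0.35, 0.25 it is 9% against 78%. For a linear effect it is 67% against 55%.

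**Identification.** A random quadratic needs 3 means + 6 (co)variances + 1 residual variance = 10 parameters. Three occasions supply 3 + 6 = 9 moments; four supply 4 + 10 = 14.

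**The case against.** The strongest reply is that the worst figures belong to a model the SAP does not spell out. Most of this stands.

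- **Arm-specific baseline.** A reader might infer that the SAP fits one. It is silent, so the 41/54/76% is conditional on the default growth model. Much of the gap to 87/89/96% comes from the baseline and not from the line: with a common baseline the slope already reaches 79/80/88%.
- **Slope as the sole test.** A reader might infer that efficacy rests on a slope. The SAP names no primary slope test. It also reports a difference at one time, tests mediation paths at discrete times and as change from baseline, and adds a Cox comparison of the post-intervention phase.
- **Effect sizes wrong at every visit.** This would need a straight line and an effect that is not linear. The SAP allows a quadratic, which cuts the error to 9% or less. With only three occasions, an arm-specific quadratic fits the mean differences exactly.
- **All later visits off treatment.** The booster session in Protocol section 8 rules out so flat a statement.
- **Model not identified.** The shortfall of 9 moments for 10 parameters arises only with three occasions. The SAP also promises to limit latent variables and keep its path models parsimonious.
- **Unknown shape and scale.** No effect shape or correlation is given, several outcomes are ordinal or counts, and the SAP calls its analyses preliminary.

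What the reply does not meet is that a common baseline costs nothing in validity under randomisation, and it raised slope power for every shape tried. Not knowing the shape is itself a reason to prefer free visit means.

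**Conclusion.** The concern holds as a conditional point about the choice and specification of the model. The SAP leaves open the baseline constraint, the time function and the visit of its main contrast, and the usual default is inefficient for this design.

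Under the assumptions listed, a common baseline alone raises slope power at ρ = 0.5 from 54 to 80% (sustained), 17 to 37% (fading) and 55 to 70% (linear). Moving to the visit average adds a further 8 to 9 points for a sustained effect and 24 to 41 points for a fading one. If the effect widens linearly, it gives up about 9 to 13 points to the common-baseline slope.

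The common baseline is therefore a clear gain. The choice of main contrast is a trade-off that depends on the expected shape. The figures are approximations for a continuous outcome with complete data; they indicate direction and rough size for ordinal and count outcomes, not exact values.

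**What to change.** First reconcile the visit schedule: Protocol section 3 and section 10 (Overview of Assessment Procedures and Attrition) against section 8. Section 10 also gives the Conduct Disorder Subscale only at intake and termination, which is too few occasions for a growth curve. Then, in the same SEM or mixed model:

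1. Constrain the two arms to a common baseline mean. This has no downside under randomisation.
2. Use free visit means, or a piecewise curve with a knot at the end of treatment, and read the time-specific difference from that model at named visits, on the link scale for ordinal and count outcomes.
3. Report the average follow-up difference, the 12-month difference and the slope difference, and name the main one in advance.
4. If the reconciled schedule leaves three occasions, do not fit a random quadratic, and correct the identification statement.

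The cost is SAP wording, with the same data and software. The one statistical price is the 9 to 13 points of power lost if the visit average is the main contrast and the effect widens linearly.

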& Wilson, 1998), they are minimally invasive, can be collected in the community during follow-up assessments and carry fewer taboos on collection (Meyers et al., 2002). Urine screen results will be kept confidential in containers marked with pre-printed labels without personal identifying information. To assure integrity of the sample, the Onsite CupKit® automatically checks for temperature, and the interviewer will ensure that there is no one else in the restroom.

Study Protocol

IRB ID: 20180597 (CR00012479)

Study Number: 1 R34 DA043784-01A1

Date: July 19, 2018

12) Data Management*

Qualitative data:

Research staff will be monitored during every step of data collection by appropriate investigators. Instruments will be reviewed periodically to insure validity and reliability. Data will be entered by our personnel into a database under the supervision of PI. Control measures will be instituted to ensure accuracy of data entry procedures prior to analysis. Also, all data will be analyzed at our data processing center, under guidelines of our data safety and monitoring plan. All written and tape-recorded materials in this study will be transcribed using Microsoft Word on a daily basis and stored in locked the PI files cabinet. They will be coded and analyzed using procedures described in Schensul et. al.

The PI, with the assistance of the project's co-Is and Post-Doctoral Associate, will analyze the data using SPSS®, STATA®, the R statistical package or relate statistical software. Outcome measures will include drug use, delinquency/crime, family functioning, educational performance, and emotional/ psychological functioning. Predictor and outcome data will be analyzed using confirmatory factor analysis, generalized linear mixed effects modeling, latent growth modeling, structural equation modeling, analysis of variance, logistic regression, and stepwise multiple regression. The significance levels will be adjusted to control for multiple outcome measures. For the primary hypotheses, power is anticipated to be .80.

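### The Vuong test is not valid for choosing between the negative binomial and its zero-inflated version, and the switch it triggers changes what the arm effect means

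*SAP*

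**What the plan says.** SAP, Analytic Methods, sets the default: "Count outcome measures (e.g., number of sexual partners, problem behaviors, re-arrests) will be analyzed using a negative binomial function". It then gives the rule for leaving that default: "Vuong tests will be performed to assess whether the data have an excess of zeros, and if necessary, zero inflated negative binomial regression" is to be used instead.

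The SAP gives no cut-off for the test and no AIC- or BIC-type correction to it. It does not list covariates for the zero part, or say whether the test is run per visit or on pooled visits. Nor does it say which coefficient is the treatment effect after a switch. The same section plans standardised effect sizes, with Cohen's d as the example, to inform a possible full trial.

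On size, the SAP's Power Analysis says "We will recruit 88 participants for this study, with the intention of analyzing data for 80 participants after attrition". Allocation is equal (Protocol section 8): "Each wave will be composed of 22 participants to be randomized into two groups (11 each"). That leaves about 40 analysed per arm. Protocol section 3 lists follow-up at 3, 6 and 12 months, so with baseline a youth can contribute up to four rows.

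**The concern.** There are two separate problems.

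First, the Vuong statistic has a standard normal reference only when the two models are non-nested. Setting the inflation probability to 0 turns the zero-inflated model into the negative binomial, so the models are nested and the null lies on the edge of the parameter space. The usual cut-off then does not have its nominal error rate.

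Second, the switch changes the question being answered. The negative binomial arm effect is a ratio of overall mean counts. The count part of the zero-inflated model gives a ratio among youths who could have a non-zero count, with a second arm effect, or none, on the zeros. One trial could therefore report an overall ratio for one count outcome and a conditional ratio for another, depending on a data-driven test.

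This matters because keeping youths at zero is part of the aim: sustained abstinence is a primary outcome (Protocol section 9), and the SAP also examines initiation of sex and drug use. It matters too because these effect sizes are meant to feed a larger trial.

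**Working it through.** **Inputs.** From the documents: n = 80 analysed and two equal arms. Assumed, because the documents are silent: mean among susceptible youths (μ), dispersion (α), structural-zero share (π), arm in the count part with constant inflation, and a one-sided Vuong cut-off of 1.645.

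**The plan's own figure.** The SAP states no operating characteristic for this rule. Its only sizing claim is "adequate levels of power (0.84 - 0.86) using a relatively simple SEM" for R² = 0.05. A single-predictor test at two-sided 0.05 does not reproduce it: f² = 0.05/0.95 = 0.0526, noncentrality 80 × 0.0526 = 4.21, power 0.53. That is a separate matter, it assumes a power model the SAP does not specify, and nothing below depends on it.

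**Step 1: why the reference fails.** Let z be the standardised evidence for inflation. Near the boundary, for z > 0, the log-likelihood gain is about z²/2 and its estimated standard error about z. The Vuong statistic is then about z/2. Requiring z/2 > 1.645 means z > 3.29, a likelihood-ratio statistic above 3.29² = 10.8. The boundary-corrected likelihood-ratio test needs only 2.706.

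**Step 2: simulation at n = 80** (300 replicates per row, maximum likelihood; Monte Carlo standard error at most about 3 points).

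| μ | α | π | Vuong > 1.645 | Boundary LR |
|---|---|---|---|---|
| 0.7 | 1 | 0 | 1.7% | 6.3% |
| 1.5 | 1 | 0 | 0.3% | 7.0% |
| 3 | 1 | 0 | 0.7% | 8.0% |
| 6 | 0.5 | 0 | 0.0% | 3.3% |
| 0.7 | 1 | 0.4 | 3.0% | 12.0% |
| 1.5 | 1 | 0.4 | 2.7% | 23.7% |
| 3 | 1 | 0.4 | 8.7% | 48.0% |
| 3 | 0.5 | 0.4 | 23.7% | 68.3% |
| 6 | 0.5 | 0.4 | 71.0% | 98.0% |
| 10 | 0.5 | 0.4 | 94.3% | 100% |

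At a 1.96 cut-off the six rows with π = 0.4 fall to 1.0%, 1.0%, 4.3%, 12.0%, 53.7% and 86.3%. Further runs show the same pattern: 4% v 22% at μ = 1 and 12% v 58% at μ = 3 (α = 0.7, π = 0.4), and 76% firing at μ = 6.

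**Step 3: what the coefficient means.** The overall mean is (1 − π)μ, so the overall ratio is (1 − π₁)μ₁ / [(1 − π₀)μ₀].

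- π from 0.30 to 0.50, μ = 6 in both arms: 0.50/0.70 = 0.714. With 20,000 simulated youths per arm, the negative binomial ratio was 0.714. The zero-inflated count ratio was 0.946 with constant inflation. With arm in both parts it was 0.999, with an inflation odds ratio of 2.36.
- Same zeros, μ from 6 to 7.5: overall (0.50 × 7.5)/(0.70 × 6) = 3.75/4.20 = 0.893, but 7.5/6 = 1.25 among the susceptible. The two point in opposite directions.
- π from 0.40 to 0.65, μ unchanged: 0.35/0.60 = 0.58 overall, 1.0 among the susceptible.

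**Step 4: the rule as written, at n = 80.** In the last example with arm in the count part only, the median reported ratio among trials where the test fired was 0.93 to 0.96, against a true overall ratio of 0.58. Over all trials under the two-stage rule the median was 0.60 to 0.65. In one run (α = 0.6, 200 replicates) rejection rates were 20.5% v 20% for the negative binomial alone at μ = 3, and 18% v 20% at μ = 4.

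**The case against.** The best defence is that the two problems offset each other. If the test seldom fires, the negative binomial is kept, which is what the fix recommends, and averaged over trials the rule costs little (step 4). That stands as a statement about averages. It does not help the particular trial in which the test fires, and at higher means firing is common.

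Several stronger readings are tempting but not supported.

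- A reader might infer that the test almost never fires at n = 80. Step 2 shows that this depends on the mean and dispersion. The SAP also does not fix n = 80 for the test: on pooled rows (80 × 4 = 320, wrongly treated as independent) it fired in 25 to 78% of runs at μ = 3, π = 0.4, with only 40 replicates.
- The z/2 argument suggests a true size of P(Z > 3.29) = 0.05%. Simulation does not bear this out at low means: 5 of 300 (1.7%) at μ = 0.7, and 5 of 200 (2.5%) at mean 1. The test is conservative, but not a hundredfold in general.
- A reader might conclude that the zero-inflated analysis will miss an effect on zeros. That requires arm to be absent from the zero part, which the SAP does not say. With arm in both parts the implied overall ratio was 0.59 and 0.57 at means 3 and 4, matching the negative binomial.
- The SAP's Analysis Rationale says "SEM generates several useful measures of overall model fit (e.g., CFI, AIC, BIC, etc", but that concerns comparing theoretical structural models. It is not an existing rule for choosing a count model.

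It is also fair that the SAP calls its analyses preliminary, that its planned hazard models examine initiation separately, and that AIC wrongly chose the zero-inflated model in 8 to 12% of no-inflation samples.

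**Conclusion.** The concern holds in a limited form. The test's normal reference is invalid for this pair of models, whatever the count means turn out to be. In the simulations it was conservative, and weaker than a boundary-corrected likelihood-ratio test that stayed near its nominal 5% (3 to 8% with no inflation). The weakness is marked for low-mean counts, which re-arrests and sexual partners may plausibly be, though the documents give no rates.

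The change of estimand is the more important part, because it follows from the two models and not from how often the test fires. After a switch, the reported ratio can sit near 1 when the overall ratio is 0.58, or point the other way. How far this misleads depends on the specification of the zero part, which the SAP leaves open. The average cost across trials is small; the cost to interpretation, and to the effect sizes carried into a full trial, is not. The sponsor should settle this before the count outcomes are analysed.

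**What to change.** Delete the Vuong switch and state three things in the SAP.

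1. For every count outcome the arm effect is the ratio of overall mean counts, from the negative binomial model with robust standard errors, clustered by youth where visits are pooled.
2. The zero-inflated model, with arm in both the count and zero parts, is a sensitivity analysis, compared by AIC/BIC or a boundary-corrected likelihood-ratio test.
3. Its result is reported as the implied overall mean ratio, (1 − π₁)μ₁ / [(1 − π₀)μ₀], beside the two component effects.

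The cost is a few sentences and some extra output. The real downside is power when a zero-inflated model would have been correctly specified. In simulation the negative binomial had 35% v 44% when the effect lay wholly in the count part, and 20% v 36 to 43% for a joint two-part test when it lay wholly in the zeros. If the sponsor expects CIFFTA to act mainly on zeros, a pre-specified joint test is a reasonable alternative, provided the effect reported is still the overall mean ratio.
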